7.3 Evaluations in case of suspension of treatment

Patients who discontinue treatment for reasons other than death and withdrawal of consent will be evaluated with a follow-up visit within 7 days of discontinuing treatment. Patients who suspend the treatment, envisaged by the protocol, will receive medical treatment as required by the clinical practice of the center.

8. EVALUATION PROGRAM

8.1 Baseline assessment before the start of radiotherapy treatment

8.1.1 Mandatory assessments:

- general and neurological examination. A palliative doctor will be supported by the radiotherapist.
- Detection of vital parameters and anthropometric indices.
- Definition of the ECOG and Karnofsky indices.
- Quality of life assessment through EORTC QLQ-C30 and BN20 questionnaires.

8.1.2 Optional assessments based on tumor site:

- neurological visit.

- Endocrinological examination with hormonal profile (FT3, FT4, TSH, FSH, LH, Estradiol (E2) if female, testosterone if male, prolactin, cortisol, ACTH, GH).
- Otolaryngological examination with complete audiometric examination (tonal and vocal).
- Eye examination with neuro-ophthalmological evaluation.
- PET with labeled amino acids or with membrane metabolism tracers.
- Other examinations and / or specialist visits depending on the particular conditions of the patient.

8.2 Evaluation at the end of the radiotherapy treatment

Clinical visit at the end of radiotherapy:

- General and neurological examination. A palliative doctor will be assisted by the radiotherapist.
- Detection of vital parameters and anthropometric indices.
- Definition of the ECOG and Karnofsky indices.
- Detection of acute toxicity via CTCAE version 4.0 scale.

8.3 Follow-up evaluation

Clinical visits at 7 days, 15 days, 30 days, 60 days and 90 days from the end of radiotherapy (RT).

8.3.1 Mandatory assessments:

- General and neurological examination. A palliative doctor will be supported by the radiotherapist.
- Detection of vital parameters and anthropometric indices.
- Definition of the ECOG and Karnofsky indices.
- Detection of acute / subacute / late toxicity by CTCAE version 4.0 scale.
- Quality of life assessment through EORTC QLQ-C30 and BN20 questionnaires (at 1 and 3 months).
- MRI of the brain before and after m.d.c. paramagnetic (1 month and 3 months from the end of RT).

8.3.2 Optional assessments based on tumor site or patient's particular condition:

- Additional specialist visits (endocrinology, ophthalmology, etc.) according to medical indications.

9. OUTCOMES EVALUATION PLAN

The response to radiotherapy treatment will be evaluated according to the RANO criteria (Technical Annex) with morphological and functional (multiparametric) brain MRI performed at 1 month after the end of radiotherapy and then after 3 months.

The toxicity assessment will be made with reference to the International Common Toxicity Criteria for Adverse Event (CTCAE) - version 4.0 (The complete document is available on the website of the National Institute of Health

The response to radiotherapy treatment will be evaluated according to the RANO criteria (Annex) with morphological and functional (multiparametric) brain MRI performed at 1 month after the end of radiotherapy and after 3 months.

The toxicity assessment will be made with reference to the International Common Toxicity Criteria for Adverse Event (CTCAE) - version 4.0 (The complete document is available on the National Institute of Health (NIH) website at the following address: <http://ctep.cancer.gov/reporting/ctc.html>), excluding neurological adverse events of grade ≤ 2 that responded adequately to supportive care.

Safety and tolerability will be defined for:

- type, frequency, severity and relationship of adverse events to treatment;
- number of subjects who prematurely discontinued treatment due to any adverse event;
- frequency of clinically significant changes and / or laboratory tests.

All patients who have started radiation treatment will be considered for analysis, until the completion of the study (i.e. until the final visit at the end of the entire program for patients who complete the treatment) or until the scheduled follow-up visit in case of premature suspension of the study. Patients will be instructed by the Investigator on the need to report any adverse events that may occur during the study.

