4. OBJECTIVES

4.1 Primary objective

The study proposes the evaluation of the side effects of the proposed experimental radiotherapy treatment and the acceptability of the risk / benefit ratio.

Acute / subacute toxicity will be analysed with recording of adverse events (related or unrelated) reported during the entire treatment and within 3 months of its end.

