5. DESIGN OF THE STUDY

It is an exploratory, prospective, experimental, monocentric study.

Having identified a main safety endpoint (toxicity of radiotherapy treatment), and in the absence of data currently available from previous studies and useful for sample sizing, the sample is defined according to criteria of expediency and feasibility, (12 cases), with a design (3 cases + 3 cases + 6 cases) which provides for two intermediate safety assessment steps, one month after the end of treatment for the third and sixth patient. The study will be continued only in the event of a positive evaluation of both steps.

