10. SAFETY ASSESSMENTS OF RADIOTHERAPY

The investigator will report all adverse events, serious and non-serious, related and unrelated within the CRF, with the exception of:

1. Any medical conditions of the patient present at baseline before the start of study treatment. Worsening of these conditions during the study will instead be recorded as an adverse event.
2. Abnormal laboratory values, unless they lead to exit from the study, a specific treatment, modification or interruption of study treatment, other therapeutic interventions or clinically important in the opinion of the Investigator. If the laboratory parameter is part of a pathological state, only the diagnosis of the same must be reported as AE within the CRF. If possible, the laboratory abnormality should be recorded as a diagnosis and not simply as an abnormal laboratory result.

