10.1 Evaluation of adverse events from radiotherapy

An adverse event (AE) is any adverse clinical event that occurs in a patient or clinical trial subject receiving treatment and which does not necessarily have a causal relationship to that treatment. An adverse event can occur in the treatment period and in the follow-up period.

An adverse event is defined as SERIOUS (SAE) if it has:

- lethal outcome;
- endangers the patient's life (it means that in the Investigator's opinion the patient is at immediate risk of death);
- imposes a hospitalization or extends the hospitalization in progress following the procedures provided for in the protocol;
- involves severe or prolonged disability or incapacity, a congenital anomaly or malformation or a birth defect;
- may endanger the subject or require intervention to prevent one of the above situations.

Within the protocol, hospitalizations already planned before the start of the protocol or as parts of the protocol, hospitalizations lasting less than 24 hours or occurring in the absence of an adverse event will not be considered serious adverse events.

For each adverse event (AE), the Investigator will provide information on the nature of the event, severity, start and end date, actions taken, causation with the treatment, seriousness and outcome.

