10.1.3 Outcome

The Investigator must indicate the action taken due to an adverse event in terms of:

- continuation of treatment;
- interruption of treatment;

indicating whether additional interventions not provided for in the protocol were necessary for the management of the event. All adverse events that did not lead to the interruption of the subject's participation in the study must be monitored until resolution of the event, partial resolution, aggravation or death (due to the event itself).

The Investigator is responsible for an adequate clinical follow-up of the event until resolution, stabilization of the event, patient death or loss of the patient at follow-up. This may mean that in some circumstances the follow-up continues even after the end of the study.

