10.2 Recording an Adverse Event

The Investigator must record any adverse events that occur during the treatment period and thereafter, up to the study closing visit in the CRF and in the relevant health records.

A completely resolved AE that recurs or increases in severity will have to be recorded as a new event within the CRF.

A description of the event will be reported with medical terms, date of presentation and resolution, severity, causation with respect to the treatment, actions taken, seriousness of the event. All the measures required for the management of the adverse event must be recorded in the reference health documentation.

If an AE is considered serious, the AE section within the CRF must be completed.

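### Section 9 leaves low-grade neurological events that responded to supportive care out of the toxicity assessment, which is the main endpoint, and nothing reconciles this with section 4.1

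*Combined protocol and SAP*

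**What the plan says.** Section 5 fixes the endpoint: "Having identified a main safety endpoint (toxicity of radiotherapy treatment"). Section 12.1 repeats that toxicity is the main endpoint. Section 4.1 gives the scope under the primary objective: "Acute / subacute toxicity will be analysed with recording of adverse events (related or unrelated"), over the treatment and the three months after it. It sets no limit by grade, organ system or response to care.

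Section 9 says that toxicity is assessed by CTCAE version 4.0, "excluding neurological adverse events of grade ≤ 2 that responded adequately to supportive care". The list that follows defines safety and tolerability by, among other things, "type, frequency, severity and relationship of adverse events to treatment", and carries no exclusion.

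On data collection, section 10 is broad: "The investigator will report all adverse events, serious and non-serious, related and unrelated within the CRF". Its two exceptions are conditions already present at baseline and certain laboratory values. For each event section 10.1 asks for "information on the nature of the event, severity, start and end date, actions taken, causation with the treatment, seriousness and outcome". Section 10.1.3 adds the action taken, "indicating whether additional interventions not provided for in the protocol were necessary for the management of the event". Section 10.2 states: "All the measures required for the management of the adverse event must be recorded in the reference health documentation".

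Section 12.2 plans tables, lists and Clopper-Pearson intervals for percentages. It names no toxicity variable, no event set and no confidence level.

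**The concern.** The plan gives the main endpoint two different scopes and does not say which one the primary tables use. An analyst following section 4.1 would count every event. An analyst following the toxicity sentence in section 9 would drop a class of neurological events.

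Three features make the narrower scope a poor basis for a primary safety result:

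- It works in one direction. Removing events can lower a toxicity count but never raise it.
- It removes only neurological events, which are of central interest when previously irradiated brain is treated again. Non-neurological events of the same grade stay in.
- Whether an event counts is settled after it has happened, by whether the response was adequate, and no criterion for adequacy is given.

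Section 2 makes safety the primary objective because clear information on toxicity in previously irradiated tissue is lacking. A headline table built on the carve-out would understate low-grade neurological toxicity, including events that needed supportive treatment.

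**Working it through.** **Comparison of scopes**

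| Place | Role | Low-grade neurological events that responded to care |
|---|---|---|
| 4.1 | Primary objective | Included (no limit stated) |
| 9, toxicity sentence | CTCAE assessment | Excluded |
| 9, safety and tolerability list | Safety definition | Included (no limit stated) |
| 10 | Recording in the CRF | Included (not among the exceptions) |
| 6.7 | Rule for continuing radiotherapy | Used to decide continuation, not counting |
| 12.2 | Analysis | Not addressed |

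No section links these scopes or assigns one to the primary tables. The toxicity sentence appears twice in section 9, and the first copy stops before the exclusion. This may be an artefact of the text, and nothing here rests on it.

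**What the exclusion reaches.** Neurological events of grade 3 or higher stay in, as do events of grade 2 or less that did not respond. The step 1 rule in section 12.1 looks at attributable toxicity above 3, so it is untouched. The step 2 rule looks at radiation-induced serious adverse events. A grade 2 neurological event could be serious through hospitalisation (section 10.1), but nothing applies the section 9 exclusion to that rule.

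**Size.** The plan has no figure to reproduce: it gives no event rate, no single toxicity rate and no formula behind the 12 patients. What follows is an illustration. Inputs: n = 12 (sections 5 and 12.1), exact Clopper-Pearson limits (section 12.2), and an assumed two-sided 95% level.

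For x events in n patients, the lower limit is the 0.025 quantile of Beta(x, n − x + 1), set to 0 when x = 0. The upper limit is the 0.975 quantile of Beta(x + 1, n − x).

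*Any-grade neurological row.* Each patient whose only neurological events are of the excluded kind lowers the row by 1/12 = 8.3 points, whatever non-neurological events that patient has. Assume 6 of 12 patients have a neurological event, and let k of them have only excluded events:

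| k | Row | 95% limits |
|---|---|---|
| 0 | 6/12 = 50.0% | 21.1 to 78.9% |
| 1 | 5/12 = 41.7% | 15.2 to 72.3% |
| 3 | 3/12 = 25.0% | 5.5 to 57.2% |
| 6 | 0/12 = 0% | 0 to 26.5% |

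*Any-toxicity percentage.* Such a patient leaves this count only if no other countable event remains. Let q be the assumed chance of another countable event. The expected drop per such patient is (100/12) × (1 − q) points:

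- q = 0: 8.33 × 1 = 8.3
- q = 0.5: 8.33 × 0.5 = 4.2
- q = 0.9: 8.33 × 0.1 = 0.8
- q = 1: 0

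**The case against.** The strongest reply is that section 9 describes two things: a restricted toxicity assessment and, separately, an unrestricted safety summary. On that reading section 4.1 is only a general objective, section 9 is the more specific rule, and the excluded events still appear in the safety tables and listings. The exclusion is prespecified and matches the category in section 6.7 under which radiotherapy continues, so it looks deliberate. It would then be enough to state which scope each table uses, and deleting the clause would be a preference.

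The two-part reading is possible, but no section states it. It also gives the name of the main endpoint, toxicity, to the restricted part, while section 4.1 describes toxicity without restriction. Section 6.7 is a rule about continuing treatment and gives no reason to leave an event uncounted.

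Other points against the concern stand in part:

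- The patient counts above are assumed. They show how far the result could move, not how far it will.
- The denominator may fall below 12, because section 7.1 removes some patients from the endpoint analysis and the study may stop after 3 or 6.
- No hypothesis test, sample size or decision threshold depends on the excluded count. The tables are nevertheless the study's main product.
- The records may not capture response cleanly. Supportive drugs permitted in section 6.8 may not count as interventions outside the protocol under section 10.1.3, section 10.2 places management measures in the health records, and resolution is not the same as adequate response. This bears only on a restricted count, which section 9 as written already requires.

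**Conclusion.** The concern holds. The toxicity assessment in section 9 is narrower than the primary objective in section 4.1, the two are not reconciled, and the narrower scope can only make the main endpoint look better. Data collection is not at fault, since section 10 records the events.

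The consequence is confined to the final descriptive toxicity results: 8.3 points off the any-grade neurological row per affected patient at n = 12, and between 0 and 8.3 points expected off an any-toxicity percentage. The total depends on how many patients have only excluded events, which the documents do not allow one to estimate, and it could be nil. The intervals assume a two-sided 95% level. The plan should be corrected before the analysis, but the point does not undermine the design or the interim rules.

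**What to change.** Delete the exclusion from the toxicity sentence in section 9. Add one sentence to section 12.2: the primary toxicity tables and their Clopper-Pearson intervals count all recorded CTCAE v4.0 adverse events. This brings section 9 into line with section 4.1.

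If the sponsor wants the restricted count as well, report it only as a secondary row labelled as such. State beforehand how an adequate response is derived from the actions, management measures and resolution recorded under sections 10.1, 10.1.3 and 10.2.

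The cost is one deleted clause and one added sentence. The primary tables need no new CRF item, and the secondary row needs no more information than section 9 already presupposes. The treatment-continuation rule in section 6.7 does not change. The reported toxicity figure may be less favourable.

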10. SAFETY ASSESSMENTS OF RADIOTHERAPY

The investigator will report all adverse events, serious and non-serious, related and unrelated within the CRF, with the exception of:

1. Any medical conditions of the patient present at baseline before the start of study treatment. Worsening of these conditions during the study will instead be recorded as an adverse event.
2. Abnormal laboratory values, unless they lead to exit from the study, a specific treatment, modification or interruption of study treatment, other therapeutic interventions or clinically important in the opinion of the Investigator. If the laboratory parameter is part of a pathological state, only the diagnosis of the same must be reported as AE within the CRF. If possible, the laboratory abnormality should be recorded as a diagnosis and not simply as an abnormal laboratory result.

10.1 Evaluation of adverse events from radiotherapy

An adverse event (AE) is any adverse clinical event that occurs in a patient or clinical trial subject receiving treatment and which does not necessarily have a causal relationship to that treatment. An adverse event can occur in the treatment period and in the follow-up period.

An adverse event is defined as SERIOUS (SAE) if it has:

- lethal outcome;
- endangers the patient's life (it means that in the Investigator's opinion the patient is at immediate risk of death);
- imposes a hospitalization or extends the hospitalization in progress following the procedures provided for in the protocol;
- involves severe or prolonged disability or incapacity, a congenital anomaly or malformation or a birth defect;
- may endanger the subject or require intervention to prevent one of the above situations.

Within the protocol, hospitalizations already planned before the start of the protocol or as parts of the protocol, hospitalizations lasting less than 24 hours or occurring in the absence of an adverse event will not be considered serious adverse events.

For each adverse event (AE), the Investigator will provide information on the nature of the event, severity, start and end date, actions taken, causation with the treatment, seriousness and outcome.

10.1.1 Severity / Severity of an event

The Investigator will have to evaluate the severity of the event on the International Common Toxicity Criteria for Adverse Event (CTCAE) classification - version 4.0, graduated on a scale from 1 to 5. In case of an event not included in the International Common Toxicity Criteria for Adverse toxicity scale Event (CTCAE) - version 4.0, the following scale will be used to indicate the severity of an event.

The severity of adverse events not listed in this classification will be assessed on the basis of the following levels:

- mild: the adverse event is easily tolerated by the subject, causing minimal discomfort and no interference with daily activities and does not require specific treatments;
- moderate: the adverse event interferes with normal daily activities but improves following therapeutic intervention;
- severe: the adverse event prevents normal daily activities and requires specific therapeutic intervention;
- life risk: immediate risk that requires hospitalization and clinical intervention;
- death.

10.1.2 Causation of an event

The Investigator is responsible for evaluating a causal link between the adverse event and the treatment, regardless of the doses administered, according to the following definitions and with respect to the information contained in the study documentation:

- not related: when the event is not considered related to the treatment (if the event is easily explained by the clinical situation, underlying diseases, concomitant therapies, specific procedures or if there is no temporal correlation);
- correlated (or possible correlation): when there are facts (evidence) or arguments that indicate or suggest a causal link (temporal relationship, nature of the event, dependence of the nature of the event on the suspension / resumption of treatment, unlikely relationship with concomitants, underlying pathologies or any procedures) between the event and the treatment.

10.1.3 Outcome

The Investigator must indicate the action taken due to an adverse event in terms of:

- continuation of treatment;
- interruption of treatment;

indicating whether additional interventions not provided for in the protocol were necessary for the management of the event. All adverse events that did not lead to the interruption of the subject's participation in the study must be monitored until resolution of the event, partial resolution, aggravation or death (due to the event itself).

The Investigator is responsible for an adequate clinical follow-up of the event until resolution, stabilization of the event, patient death or loss of the patient at follow-up. This may mean that in some circumstances the follow-up continues even after the end of the study.

10.2 Recording an Adverse Event

The Investigator must record any adverse events that occur during the treatment period and thereafter, up to the study closing visit in the CRF and in the relevant health records.

A completely resolved AE that recurs or increases in severity will have to be recorded as a new event within the CRF.

A description of the event will be reported with medical terms, date of presentation and resolution, severity, causation with respect to the treatment, actions taken, seriousness of the event. All the measures required for the management of the adverse event must be recorded in the reference health documentation.

If an AE is considered serious, the AE section within the CRF must be completed.

10.3 Intermediate safety reports

The investigator will produce a safety report as per the analysis plan defined in paragraph 12.1 and upon request to be submitted to the internal board and / or the Ethics Committee.

